While blood extraction with a jet injector has not yet been trialled, one study investigated the ability of a jet injector to extract interstitial fluid [4]. This study attempted to collect the fluid back through the same small orifice through which the jet was formed, and waited less than 0.5 seconds between breaking the skin and collecting the fluid. The volume of fluid collected ranged between 10 μ L and 40 μ L but was found to be mainly derived from the fluid that was injected, with interstitial fluid making up between 1% and 3%. As demonstrated by this study, we anticipate that one of the major problems with obtaining a capillary blood sample using jet injected fluid. As part of this study we wish to investigate the extent of this dilution issue. We propose to measure the dilution by marking our injected fluid with indocyanine green (ICG), an FDA approved fluorescent marker. By exciting the retrieved blood samples with 780 nm light, and measuring the resulting fluorescence we will be able to measure the dilution of the sample.

ICG is commonly used for diagnostic purposes (e.g., cardiocirculatory, retinal and liver function diagnostic tests), typically at a dose of no more than 2 mg/kg and a concentration of 5 g/L [5]. ICG has been delivered transdermally into the subcutaneous tissue in multiple fluorescent lymphography studies, and into the dermal layer in a recent study performing fluorescent microscopy. Delivery of 20 μ L of 5 g/L ICG into the dermis was described as having a "short-time tolerable burning sensation" [6], but in this study we plan to use a concentration of only 10 mg/L.

2. Research Aims

In this study we intend to use needle-free jet injection not to deliver a drug, but instead just to pierce the skin with a small volume of isotonic saline or ICG solution, and then retrieve a capillary blood sample. Ultimately we believe a single jet injection device may be able to extract blood, perform a blood glucose measurement and then, based on this measurement, deliver the ideal volume of insulin. However, this study will focus only on establishing the ability of this technique to achieve a measurement of blood glucose concentration.

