3.2. Population & Recruitment

We intend to recruit up to 35 healthy participants to take part in this study. These participants will be divided into two groups with up to 25 participants in the first group and up to 10 in the second. The difference between these groups relates to the measurements that will be made on their blood samples, and also in the injectate used to obtain these measurements. The samples gathered from participants in the first group, using isotonic saline for the jet injections, will be tested for glucose concentration, while those from the second group, using isotonic saline with ICG for the jet injections, will have a fluorescent based dilution measurement. Participants will be aware that the study is structured in this way, and will be aware of which group they are being recruited into.

With a minimum sample size of 20 in the first group we predict we will be able to distinguish statistically significant differences between groups whose mean dilution differs by as little as 10% ($\sigma_{glucometer}$ =0.6 mmol/L, α =0.05, β =0.1). We predict we will be able to observe differences in mean dilution as low as 5% in group 2 with a sample size of at least 8 ($\sigma_{fluorimeter}$ =3%, α =0.05, β =0.1). Sample volume is measured identically across both groups and we predict we will be able to observe differences in mean volume released as low as 0.84 µL ($\sigma_{BloodVolume}$ =1 µL, α =0.05, β =0.1).

The study will be advertised within the Auckland Bioengineering Institute and Department of Engineering Science. This will involve flyers posted within Auckland Bioengineering House ([name]) and an email sent to the Auckland Bioengineering Institute. These advertising materials will recommend that anybody interested in participating get in contact with the researchers for more information. In response to expressions of interest the researchers will provide a copy of the participant information sheet (PIS) and consent form (CF) to give detailed information about the study. Participants will be asked to take their time reading these forms and, if they are interested in participating, to indicate times that might suit them to come in for the study. This will also allow potential participants adequate opportunity to ask questions and seek external advice regarding participation in the study.

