3.4. Interventions

Each participant will be subjected to four interventions: a standard lancet prick, a jet injection with a standard circular orifice, and two jet injections with different custom slot orifices. These interventions will be performed on the side of the fingertip of the middle (3rd finger) and ring finger (4th finger) of either hand. Which finger receives which intervention will be randomised, as will the order of the interventions. The participants will be blinded by an opaque barrier which will prevent them observing the procedure but allow them to see and communicate with the practitioner. After each intervention has been applied, and the associated blood samples collected, there will be a 2 minute 'break' before performing the next intervention. The participants will be shown the jet injector and lancing device following the procedures. The interventions will be identical for both groups with the exception of the fluorescent dye (ICG, 0.01 mg/L) added to the jet injected fluid for group 2.

Lancet

Capillary blood will be sampled in accordance with the "WHO guidelines on drawing blood" [8]. This will involve a lancet piercing the skin to a depth of 2.3 mm. The collection of the blood into four sequentially-collected samples differs from the WHO guidelines, but is necessary to the study (see section 3.5), and adds no extra risk to the participant.

Jet Injection

A jet injection of less than 50 μ L of sterile isotonic saline will be performed to pierce the skin. The jet will target the same depth in the dermis as the lancet (2.3 mm). Similarly to the lancet, the jet injector based blood sampling will be done as closely as possible to the WHO guidelines. However, the use of a jet injector itself is not currently within these guidelines, as this is novel to this study.

For group 2 ICG will be added to the injected saline to a concentration of (10 mg/L). An ICG concentration of 10 mg/L is well below the dose used for other diagnostic procedures (5 g/L) approved by the FDA.

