3.6. Measurements

Volume

The blood will be collected from the skin using capillary tubes. As the dimensions of these capillary tubes are known the sample volume will be measured by the length of tube that is filled with blood.

Group 1: Glucose Concentration

For the samples collected on participants from group 1 we will then measure the glucose concentration of each blood sample. This will be done using a CareSens N point of care glucometer. This approved (and Pharmac funded) device involves the blood sample being collected onto a single use test strip inserted into the glucometer. The dilution of the blood samples collected following the jet injections will be implied by comparing the glucose concentration with that measured on the control (lancet) samples. The blood samples will be disposed of as medical waste following this glucose measurement.

Group 2: Blood Dilution (Fluorescence)

For group 2 after the volume is measured, we will measure the ICG concentration in the sample using a benchtop fluorimeter that has been developed at the Auckland Bioengineering Institute specifically for this purpose. The capillary tube containing the blood sample will be placed into the fluorimeter, which will excite the sample with 780 nm light. The resulting fluorescence will be measured, indicating the concentration of ICG and hence the proportion of injectate in the blood sample.

As the fluorimeter requires a sample of 10 μ L to produce a reliable measurement, and we expect our samples to typically be around 5 μ L, we will pre-mix the samples with isotonic saline solution. We will mix a volume of saline rounded up to the nearest 1 μ L with our sample to ensure a total volume of at least 10 μ L. In samples where the initial volume is greater than 5 μ L the added volume of saline will be equal to the sample volume rounded up to the nearest 1 μ L. This will ensure all samples will end up in the ideal concentration range of 0 mg/L – 5 mg/L for measurement of ICG with this device. The samples will be weighed following this mixing to quantify the volume that was added. The fluorescence measurement, initial sample volume, and mixed volume will then be used to calculate the ICG concentration, and therefore the blood volume, in the initial sample.

Perceived Pain

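### Group 1 turns a glucose fall into a dilution percentage, but the protocol does not show that the two are equal on this strip meter

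*Protocol*

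**What the plan says.** Protocol section 3.6 names the Group 1 instrument: "This will be done using a CareSens N point of care glucometer". Of the dilution it says only this: "The dilution of the blood samples collected following the jet injections will be implied by comparing the glucose concentration with that measured on the control", meaning the lancet. It does not state the meter's calibration basis or haematocrit response, and it describes no conversion from glucose to injectate share and no check on saline-diluted blood.

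For Group 2 the same section measures fluorescence, "indicating the concentration of ICG and hence the proportion of injectate in the blood sample". It gives an operating range of 0 to 5 mg/L, a pre-mixing rule and a back-calculation.

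Section 3.2 plans Group 1 (at least 20 participants) to "distinguish statistically significant differences between groups whose mean dilution differs by as little as 10" per cent, with an SD of 0.6 mmol/L, α = 0.05 and β = 0.1. For Group 2 (at least 8) it gives 5% with an SD of 3%. Both are called mean dilution.

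On how much dilution to expect, section 3.4 says "A jet injection of less than 50 μ L of sterile isotonic saline will be performed to pierce the skin" and section 3.6 adds "we expect our samples to typically be around 5 μ L". The injected volume can therefore be several times the sample volume.

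**The concern.** One term covers two quantities. In Group 2, dilution is the volume share of injectate. In Group 1 it is a relative fall in a meter reading. The two are equal only if the reading falls in exact proportion to the injected share.

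There are two reasons why it might not. If the strip senses glucose in plasma or in blood water, saline dilutes that phase by more than it dilutes the whole sample. Saline also lowers the haematocrit, and a haematocrit-sensitive strip may then read too high or too low. The lancet sample contains no saline, so any such error sits in the jet samples alone and does not cancel in the comparison.

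At stake are the sizes of the effects in questions (b) and (c) of section 2.1: how much dilution there is, how it changes from 10 to 40 s, and how far slot and circular orifices differ.

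**Working it through.** **1. The planning figures.** The two-sided two-sample normal approximation uses 1.960 + 1.282 = 3.242.

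- Group 2: n = 2 × (3.242 × 3 / 5)² = 7.6, so 8. This reproduces the protocol.
- Group 1: detectable difference = 3.242 × 0.6 × √(2/20) = 0.615 mmol/L. To call this 10%, the reference glucose must be 0.615 / 0.10 = 6.15 mmol/L, which the protocol does not state. If 0.6 were the SD of paired differences, the detectable difference would be 3.242 × 0.6 / √20 = 0.435 mmol/L, and the implied reference 4.35 mmol/L.

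So the 10% is a relative glucose difference. It is neither confirmed nor refuted as long as its reference level is missing.

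**2. From injectate share to apparent glucose fall.** Let f be the true volume share of glucose-free saline and H the haematocrit of the undiluted blood. The documents give neither H nor the meter's behaviour. The following are assumptions: H = 0.36 to 0.50; water fractions of 0.93 (plasma) and 0.71 (red cells); and a haematocrit effect b of 0 to 1% of the reading per haematocrit point lost, raising the reading.

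| Assumed meter behaviour | Apparent fall | f = 10% | f = 20% | f = 50% |
|---|---|---|---|---|
| A. True whole-blood glucose | f | 10.0% | 20.0% | 50.0% |
| B. Plasma, no exchange with red cells | f / [f + (1−H)(1−f)] | 14.8–18.2% | 28.1–33.3% | 61.0–66.7% |
| C. Water phase, full equilibration, w = 0.93(1−H) + 0.71H | f / [f + w(1−f)] | 11.6–11.9% | 22.7–23.4% | 54.0–54.9% |
| D. Whole blood with haematocrit effect b | 1 − (1−f)(1 + b × 100Hf) | 5.5–10.0% | 12.0–20.0% | 37.5–50.0% |

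The extremes at f = 0.10 and H = 0.50 are:

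- B: 0.10 / (0.10 + 0.50 × 0.90) = 0.10 / 0.55 = 18.2%.
- D with b = 0.01: the haematocrit falls by 5 points, and 1 − 0.90 × 1.05 = 5.5%.

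**3. The reverse direction.** An apparent 10% means:

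- under B at H = 0.50, f = 0.10 × 0.50 / (0.90 + 0.10 × 0.50) = 0.05 / 0.95 = 5.3%;
- under D at H = 0.50 and b = 0.01, (1−f)(1 + 0.5f) = 0.90, so f² + f − 0.2 = 0 and f = 17.1%.

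**4. Effect on a contrast.** Take two orifices with true shares of 10% and 20%, a gap of 10 points. Under B at H = 0.50 the apparent gap is 33.33 − 18.18 = 15.2 points. Under D at H = 0.50 and b = 0.01 it is 12.0 − 5.5 = 6.5 points.

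**5. What is preserved.** At f = 0 every formula gives zero, so the lancet control carries no error that could cancel. In all four models the apparent fall rises with f. For D at its extreme it equals 0.5f + 0.5f², which is increasing. The direction of a change over time or between orifices therefore survives; its size in percentage dilution may not.

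**The case against.** **The bias is not demonstrated.** This stands. A reader might infer that the Group 1 percentages are definitely biased, or that glucose always falls by more than the injected share. The documents support neither reading. Model A is exactly one-for-one, B and C overstate dilution, and D understates it.

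**No formula is written, and a conversion could sit in an SAP that is not shown.** This stands in part. The text speaks only of a comparison, with no explicit ratio. But whether a strip meter responds in proportion on saline-diluted blood is a question of measurement method. Section 3.6 deals with such matters for Group 2 and has no counterpart for Group 1. Section 3.2 already expresses the glucose-based result as percentage dilution.

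**Heavy dilution is not predicted.** A reader might take the earlier study cited in the Background, whose fluid was "mainly derived from the fluid that was injected, with interstitial fluid making up between 1% and 3" per cent, and conclude that Group 1 readings would disappear below the glucometer SD. The documents do not support this. That study drew interstitial fluid back through the jet orifice within 0.5 s, whereas this trial collects blood from the skin at 10 to 40 s. A planning SD is also not a detection limit.

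**The groups are never pooled.** This stands. A reader might expect the two groups to appear to disagree, but the protocol plans no numerical comparison of their percentages.

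**The principal question is about a glucose measurement.** This also stands, and it limits the consequence.

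**Conclusion.** The point holds in a limited form. The protocol labels a relative glucose fall as dilution, and uses the same word for Group 2's injectate share, without showing that the two are equal on this meter. Under the stated assumptions a true 10% share could read as about 5.5% to 18.2%, with no bias if the meter reads true whole-blood glucose. The sizes of the Group 1 time trend (b) and orifice contrasts (c), expressed as percentage dilution, are therefore of unknown bias and direction.

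The direction of trends is preserved as long as the meter's reading falls steadily with dilution, as it does in every model tried. The glucose reading that the principal question needs is not affected. All haematocrit, water-fraction and meter-bias values are assumptions, so the range shows what is possible and does not estimate the bias. The point should be corrected, but it does not threaten the study's main aim.

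**What to change.** **In 3.6, choose one of two routes.**

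1. Report the Group 1 result as the relative glucose reading, jet versus lancet, and base statements on percentage dilution on Group 2. This is a change of wording only. The downside is that those statements then rest on the smaller group (up to 10 participants, against up to 25).
2. If Group 1 is also to give percentage dilution, first run a short bench series on the same strips with blood mixed with known saline fractions. Use more than one haematocrit, since participants' haematocrit is not measured. Convert readings through that curve, and report those beyond its usable range as dilution of at least X%, not as point values. The likely cost is a few dozen strips and about half a day of bench work, plus a source of blood for the bench. It adds no procedure for participants.

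**In 3.2,** restate the Group 1 10% as a difference in measured glucose and give the reference glucose and comparison it assumes. About 6.15 mmol/L reproduces it for a two-sided two-sample comparison at n = 20. Keep mean dilution for Group 2, unless route 2 is taken. This is a change of wording only.

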3.7. Materials

Lancet

The lancing will be performed using a standard, commercially available tool (Accu-Check, Safe-T-Pro-Plus). This will be set to penetrate to a depth of 2.3 mm. This device shields the lancet following penetration, making accidental stick injury extremely unlikely.

Jet Injector

The injection system has been designed in accordance with medical electrical equipment safety standard IEC 60601-1. The jet injector includes an electric motor which is momentarily (<0.1 s) supplied with a voltage (<320 V) to perform the injection. All elements of the injector that are exposed to the user are made from plastic and as such, in the very unlikely event of a short circuit within the injector, it is not possible for the participant or researcher to be exposed to the driving voltage. It would require a minimum of three simultaneous faults to expose a participant or researcher to any electrical current. During use all external surfaces of the device remain well below the maximum temperature (40 $^{\circ}$ C) dictated by the IEC 60601-1 standard.

The orifices and ampoules used with the injector must be sterile as they will be in contact with the participant and the injectable fluid. The ampoules with the standard circular orifices come in sterile packaging and will be single use. The custom slot orifices and ampoules are made at the Auckland Bioengineering Institute and will be reused through the trial. This equipment will be cleaned according to AS/NZS 4187:2014, and sterilised using a class B autoclave following use on a participant (and prior to the first use). Similarly to standard medical syringes, a small amount of medical grade silicone lubricant will be used to lubricate the interior of the ampoules.

Injectate

The jet injections will be performed using a volume of less than 50 μ L of sterile isotonic saline. For group 2 this will include ICG at concentration of 10 mg/L. ICG is an FDA approved, fluorescent marker which is commonly used at a concentration of 5 g/L. We will deliver ICG at a concentration five hundred times smaller than this. The ICG solution will be used as a marker that will allow us to measure the dilution of blood samples.

Blood collection/containment

The blood forming at the intervention sites will be collected using disposable capillary tubes. For samples from group 1 the blood will then be ejected from the capillary tubes onto a glucose test strip. While the capillary tubes containing the blood collected in group 2 will be placed directly into the fluorimeter. All samples and capillary tubes will be disposed as medical waste following collection and measurement.

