This work will test the ability of a needle-free jet injection device to release capillary blood in order to measure glucose concentration. We wish to evaluate how this technique compares to the current best practice where the skin is broken with a lancet. We will compare jet injections performed with a standard circular orifice and two custom orifices that produce jets of rectangular shape ('slot' orifices). The custom slot orifices are designed to mimic the shape of the puncture made by a lancet in the skin, and we hypothesise that this may assist in obtaining a blood sample with the jet injector. The comparisons will require measurement of the volume of blood released, blood sample dilution, blood glucose concentration, and participant discomfort.

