2.1. Principal Research Question

"Can a needle-free jet injection device be used to obtain a capillary blood sample for a glucose concentration measurement?"

This can be broken down into five further questions which relate directly to the measurements we will be making:

- a) Does a jet injector release a similar volume of capillary blood relative to a lancet?
- b) Does the use of a jet injector dilute the capillary blood sample, and, if so, how does this dilution change over time as blood is released?
- c) Does a slot orifice help release more blood than a circular orifice? And is the dilution of the collected blood different for jet injection with a slot orifice versus a circular orifice?
- d) Is the use of a jet injector for this purpose associated with similar, or lesser, levels of discomfort relative to a lancet?
- e) Does a jet injection lead to any significantly different skin reactions at the intervention site relative to a lancet prick?

3. Research Methods

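### Question (c) is worded as orifice shape, but slot and circular hardware also differ in source and reuse, so a difference cannot be credited to shape alone

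*Protocol*

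**What the plan says.** Protocol section 2.1, question (c), asks "Does a slot orifice help release more blood than a circular orifice" and whether dilution differs between the two. Section 2 supplies the mechanism: "The custom slot orifices are designed to mimic the shape of the puncture made by a lancet in the skin", with the hypothesis that this may help in obtaining a sample.

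Section 3.4 lists the four interventions each participant receives: "a standard lancet prick, a jet injection with a standard circular orifice, and two jet injections with different custom slot orifices". Finger and order are randomised.

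Section 3.7 (Jet Injector) then describes the hardware:
- Circular: "The ampoules with the standard circular orifices come in sterile packaging and will be single use".
- Both slots: "The custom slot orifices and ampoules are made at the Auckland Bioengineering Institute and will be reused through the trial". They are cleaned and autoclaved after use on a participant.

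The protocol does not state how many units of each slot design there are, how often a unit may be reused, or whether unit and use number are recorded. It mentions no bench check that the two kinds of ampoule behave alike apart from orifice shape.

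**The concern.** The contrast of interest is shape. The contrast that the design delivers is shape, source and use history together. That matters in two ways.

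1. **Attribution.** If in-house manufacture, or repeated cleaning and autoclaving, changes the jet, the change appears in the slot arms and not in the circular arm, in every participant. Randomising finger and order cannot remove it, and neither can using participants as their own controls.
2. **Precision.** The circular arm uses a new ampoule each time, so unit-to-unit variation averages out over participants. A slot arm rests on however many units are reused. With up to 35 participants, a single unit of one design could be used up to 35 times. Whatever is peculiar to that unit is shared by everyone treated with it, and more participants do not dilute it. A standard error computed over participants leaves this component out.

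At stake is what may be concluded on question (c), and possibly which orifice is carried into later device work.

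**Working it through.** **Is the overlap complete?** Code the four arms with an intercept and three contrasts (jet versus lancet, slot versus circular, slot 2 versus slot 1), then add an indicator for in-house, reused hardware:

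| Arm | Slot vs circular | In-house, reused |
|---|---|---|
| Lancet | 0 | 0 |
| Circular | 0 | 0 |
| Slot 1 | 1 | 1 |
| Slot 2 | 1 | 1 |

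The two columns are identical. The design matrix has rank 4 without the indicator and rank 4 with it, so no analysis of these arms can separate shape from source. A use-number column, if recorded, raises the rank to 5. A trend with reuse could then be estimated, but the manufacture difference still could not.

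**The plan's own volume figure.** Section 3.2 gives a detectable difference of 0.84 µL with SD 1 µL, α 0.05 and β 0.1. It states no sample size for volume.
- n per arm = 2 × (1.960 + 1.282)² × 1² / 0.84² = 29.8, so 30 (two-sided, unpaired).
- At n = 30: SE = √(2/30) = 0.258 µL, and the detectable difference is 3.242 × 0.258 = 0.837 µL. The figure is reproduced.
- The two stated minimums, 20 + 8 = 28, give 0.866 µL, and power of 0.88 at 0.84 µL.

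**Illustration 1: fixed hardware offset b, no shape effect.** P(significant) = P(|Z + b/0.258| > 1.96). The values of b are assumptions. For scale, 0.25 µL is 5% of the typical 5 µL sample in section 3.6.

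| b (µL) | n = 28 | n = 30 | n = 35 |
|---|---|---|---|
| 0.10 | 0.066 | 0.067 | 0.070 |
| 0.25 | 0.155 | 0.162 | 0.182 |
| 0.50 | 0.465 | 0.491 | 0.552 |

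(The SE is √(2/n) at each n.)

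**Illustration 2: slot units vary with SD τ, k units share the participants equally.** Error rate = 2 × P(Z > 1.96 / √(1 + τ²/(k × SE²))), with SE² = 2/30 = 0.0667. For τ = 0.25 and k = 1: τ²/SE² = 0.0625/0.0667 = 0.9375, √1.9375 = 1.392, 1.96/1.392 = 1.408, giving 0.159. Both τ and k are assumptions.

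| τ (µL) | k = 1 | k = 2 | k = 4 |
|---|---|---|---|
| 0.25 | 0.159 | 0.106 | 0.078 |
| 0.10 | 0.068 | 0.059 | 0.054 |

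**Effect of pairing.** Both illustrations use the unpaired SE that matches 0.84 µL. With an assumed within-participant correlation of 0.5, SE = √(2 × 0.5/30) = 0.183 µL, and a 0.25 µL offset gives about 28% instead of 16%.

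Dilution, the other half of question (c), was not sized. The overlap of shape with source is the same there.

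**The case against.** The protocol is open about this. It labels the arms standard circular and custom slot throughout and states single use against reuse. Read as a comparison of those hardware sets as used, the estimate is valid, and the shape hypothesis is tentative. The study is a feasibility pilot whose principal question is jet against lancet; (c) is one of five sub-questions. All jet arms share the injection system, the 2.3 mm target depth and the limit of under 50 µL, and the lubricant statement makes no distinction by ampoule type. Because there are two slot designs, a fault in one slot unit need not appear in the other. How unit and use number are analysed could sit in an analysis plan that is not shown.

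Much of this stands. The shared features reduce the risk, and agreement between the slots is a partial check on unit-specific faults, though not on a manufacture or reuse effect common to both. But question (c) and its rationale are worded as shape, and no later analysis plan can separate shape from manufacture with these arms. Nor can it use unit and use numbers that nobody wrote down.

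A reader might infer that the error rate for (c) does exceed 5%, or that the slot result is biased. The documents do not support either: every offset and unit SD above is assumed, and at τ = 0.1 µL the inflation is slight. A reader might also infer that several units with a random unit effect would cure the problem. That handles variation between units and leaves the manufacture difference where it is.

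**Conclusion.** The point holds as a limit on interpretation. Source and reuse coincide completely with the slot-versus-circular contrast, so a difference in volume or dilution cannot be attributed to shape alone. This follows from sections 2.1, 3.4 and 3.7 and needs no assumption about size.

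Whether the error rate is affected is conditional: it would exceed 5% if slot units differ or wear. On assumed values the rate is about 16% for a 0.25 µL offset, about 16% for a unit SD of 0.25 µL with one unit per design, and 5% to 7% for a unit SD of 0.1 µL. These rest on SD 1 µL, 30 per arm and an unpaired SE. The documents say nothing about the existence or size of such an effect, or about the number of units. The slot 1 versus slot 2 comparison is not affected by the difference in source, since both are made in-house and reused.

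**What to change.** In section 3.7, before data collection:
- Record slot unit identity and use number at every injection.
- Where more than one unit of a slot design exists, use them in rotation.
- Check for a trend with use number and for differences between units.

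State the conclusion to (c) as reused in-house slot ampoule versus single-use standard circular ampoule. The shape wording can be kept if a circular orifice made and reprocessed in the same in-house way serves as the comparator. That comparator, and any set minimum number of units, is optional, because the documents do not show what extra parts would cost.

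Cost: two extra fields on the injection record, a small extra analysis, and a narrower claim for (c). The record has to be in place from the first injection, since use history that was not logged may not be recoverable.
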